7.1 Subject Disposition

All subjects who were screened in the study will be summarized in a frequency distribution table by their following status after the baseline visit where the denominator will be the number of subjects screened:

- Screened and Treated
- Screened and Not Treated

Any subjects “Screened and Not Treated” will be subcategorized for the following reasons collected on the CRF: does not meet inclusion/exclusion criteria, withdrew consent, adverse event, protocol non-compliance, lost to follow-up, pregnancy, sponsor terminated the study, and other. “Other” will be displayed on the tables if collected on the CRF and no other standardized term may be used.

Frequency distributions of the subjects who completed each treatment period and the overall study will be summarized. Furthermore, frequency distributions for the subjects who discontinued prematurely will be summarized along with the primary reason for withdrawal or discontinuation collected on the CRF.

The subject disposition listings will include all subjects with the following data: date informed consent signed, IRB approval date, date of completing or discontinuing from the study, date of last dose of study drug (if applicable), study completion status, and primary reason for study discontinuation (if applicable), and the date of the follow-up visit or reason why it was not done. Subjects who received study drug will have their calculated study days presented next to the dates in parentheses.

7.2 Demographics and Disease History

Demographics and baseline characteristics will be summarized for the safety, efficacy, and PP populations. Descriptive statistics will be calculated for the following continuous demographic and baseline characteristic variables at screening: age, height, weight, and body mass index (BMI). Frequency distributions will be tabulated for the following categorical demographic variables: sex, childbearing potential, race, and ethnicity. Sex will be listed and summarized in the tables even though all the subjects screened for this study are females.

The onset disease history for fibromyalgia will be summarized based on the number of years in the demographics and baseline characteristics table. The fibromyalgia event will also be provided in the medical history subject listing, but not in the summarized in the medical history table.

The number of years for fibromyalgia be calculated as the (number of days from the onset date to the latest signed informed consent date) / 365.25 rounded off by one number after the decimal point. For partial dates collected, the imputation fibromyalgia onset date described in [Section 5.6.3](#) will be used.

Subject listings will include the subject's date of birth, any reasons why the subject does not have childbearing potential (if applicable), and all continuous/categorical variables listed above.

7.3 Subject Inclusion and Exclusion Criteria

Inclusion and exclusion criteria will be provided in a subject listing where each subject number not meeting each criterion will be displayed. The inclusion/exclusion criteria numbers not met will be listed with a brief description of the inclusion/exclusion criteria.

7.4 Medical History

Medical history data will be mapped using the Medical Dictionary for Regulatory Activities (MedDRA, version 19.0 to system organ class (SOC), and preferred term (PT). This data will be summarized in a frequency distribution. Subjects may have more than one medical history record per SOC and PT. At each level of subject summarization, a subject will be counted once if he/she reports one or more medical history record at that specific level. Subjects must have a medical history of fibromyalgia in order to be eligible for the study. Therefore, fibromyalgia will not be counted in the medical history frequency distribution table, but a footnote will be added that all subjects had fibromyalgia in the safety population. A frequency distribution table will be displayed by each study drug treatment period received and all subjects even though the medical history information was collected prior to dispensing study drug.

Additionally, collected data on the CRF will be listed by subject, verbatim body system, verbatim medical condition/procedure, onset date, and ongoing status/end date.

8. Study Drug Exposure and Other Medications

8.1 Study Drug Accountability

Subjects will be dispensed study drug based on fixed treatment periods at visits Day 1 (Baseline), Week 2, and Week 4. In the event the subject comes in for an unscheduled visit prior to a weekly visit, they may be dispensed additional study drug. Additional study drug may be dispensed at any study visit or unscheduled visit if the subject will need study drug beyond the two week allotment

provided at Day 1, Week 2 and Week 4. Capsule strengths for NYX-2925 are 10 mg and 100 mg. Subjects will be instructed to take 2 capsules of investigational product once daily by mouth.

The following data will be collected and derived at each start and end to the study drug accountability treatment periods/visit intervals:

Parameter	Origin/Derivation
Capsules Dispensed Amount	CRF
Capsules Returned Amount	CRF
Expected Number of Capsules Taken	Derived: Date Returned – Date Dispensed + 1 (where the maximum would be 30 because 30 capsules are issued at each dispensing visit)
Estimated Number of Capsules Taken	Derived: Number of Capsules Dispensed Amount – Number of Capsules Returned Amount
Treatment Compliance (%)	Derived: $100 \times \frac{\text{Estimated Number of Capsules Taken}}{\text{Expected Number of Capsules Taken}}$ (rounded off by one number after the decimal point)

The Overall NYX-2925 Treatment Compliance (%) will be calculated as:

- $100 \times \frac{\sum (\text{Estimated Number of Capsules Taken at All Study Drug Return Visits After NYX-2925 20 mg or 200 mg PO QD was Dispensed})}{\sum (\text{Expected Number of Capsules Taken at All Study Drug Return Visits After NYX-2925 20 mg or 200 mg PO QD was Dispensed})}$ and rounded off by one number after the decimal point

A subject will be classified as being compliant with study drug administration if their calculated compliance by each treatment period and overall is between 80% and 125%, inclusive. Descriptive statistics will be summarized for treatment compliance by returning analysis visits Week 2 (Placebo), Week 4 (NYX-2925 20 mg PO QD), Week 6 (NYX-2925 200 mg PO QD), and Overall (NYX-2925 20 mg and 200 mg PO QD). The following categorical ranges will be summarized in a table for those same analysis visits and overall:

- <80%, 80-125%, >125%, and Not Reported

Any study drug not returned during a subject's visit where study drug compliance is assessed will assume that all of that study drug was taken by the subject for analysis purposes. No adjustments will be made even if comments are documented on the CRF that stated lost samples were reported by the subjects. All study drug accountability comments will be provided in a subject listing. If a subject is lost to follow-up after being dispensed study drug, then the study drug returned and overall treatment compliance will be set to missing. Any unscheduled visits will be summarized within the study treatment periods based on the study drug dispensed (Placebo, NYX-2925 20 mg PO QD, or NYX-2925 200 mg PO QD).

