6.2 Efficacy Population

The efficacy population will be based on subjects included in the safety population and have at least one post-baseline visit after receiving NYX-2925 20 mg PO QD. Subjects in the efficacy population will be analyzed based on the planned treatment they were supposed to receive within each treatment period. The efficacy population will be the primary analysis population used for this study.

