6.3 PP Population

The Per Protocol (PP) population will be based on all subjects in the efficacy population and the following criteria:

- Subjects first received Placebo for 2 weeks, then NYX-2925 20 mg PO QD for 2 weeks, and then NYX-2925 200 mg PO QD for 2 weeks;
- Subjects received the appropriate study drug for each treatment period;
- Subjects did not use any of the prohibited concomitant medications listed in Section 8.8 of the protocol;
- Subjects who have an overall NYX-2925 study drug treatment compliance between 80% and 125%;

Subjects in the PP population will be defined based on a review of the relevant data by the Sponsor prior to database lock and subjects may be excluded due to particular major protocol deviations.

Subjects in the PP population will be analyzed based on the planned treatment they were supposed to receive within each treatment period.

7. Disposition, Baseline, and Other Characteristics

All subjects will be summarized in the tables based each study treatment they were dispensed and received. The maximum strength study drug dose received, “Screen Failure” or “Not Treated” will be displayed in the subject listings.

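### SAP 8.1 divides capsules taken by days elapsed although two capsules are due each day, so full adherence over a 14-day interval scores 186.7% and fails the 80–125% compliance and PP band

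*SAP*

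**What the plan says.** SAP 8.1 builds treatment compliance from two derived quantities. The estimated number of capsules taken is the number dispensed minus the number returned. The expected number is "Date Returned – Date Dispensed + 1 (where the maximum would be 30 because 30 capsules are issued at each dispensing visit" (the bracket closes there in the SAP). Compliance is 100 times the first divided by the second. Overall NYX-2925 compliance is the ratio of the sums over the 20 mg and 200 mg periods.

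The same section gives the regimen: "Subjects will be instructed to take 2 capsules of investigational product once daily by mouth". The protocol synopsis agrees, with two capsules once daily for placebo, for 20 mg (two of 10 mg) and for 200 mg (two of 100 mg). Protocol 8.2 gives 30 capsules per bottle.

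A subject is compliant if the "calculated compliance by each treatment period and overall is between 80% and 125%, inclusive". The tables use the categories below 80%, 80–125% and above 125%. SAP 6.3 makes overall NYX-2925 compliance within the same limits a condition for the PP population.

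**The concern.** The ratio mixes units: capsules over days. With two capsules due each day, the denominator is half of what its name says. The stated maximum shows what was meant. A limit of 30 justified by the capsules issued makes sense only for a capsule count, and a two-week interval reaches it only with the missing factor: 2 × (14 + 1) = 30. No other visible passage supplies that factor.

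The effect is more than a shift in percentages, because fixed limits are applied to the result. Adherent subjects would be reported as taking more than 125% of their drug and would fail the PP criterion. Subjects who missed roughly a third to over half of their capsules would be called compliant and would meet it. With about 24 subjects planned (SAP 4.3), a PP population programmed literally could be nearly empty, or made up of the less adherent subjects.

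**Working it through.** The plan gives no worked compliance figure, so there is none to reproduce.

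**Inputs**
- Two capsules per day in all three periods (SAP 8.1; protocol synopsis).
- 30 capsules per bottle (protocol 8.2). Drug is dispensed at Day 1, Week 2 and Week 4, and more may be dispensed if needed (SAP 8.1).
- Target days 14, 28 and 42 for Weeks 2, 4 and 6 (SAP 5.5.1), so each NYX-2925 period is 14 days from dispensing to return.
- Visit windows of ±2 days (protocol, headings of 10.2.2 to 10.2.7). If both visits move, a NYX-2925 interval runs from 10 to 18 days.

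Let *d* = return date − dispensing date. As written, compliance = 100 × capsules taken / (*d* + 1). The maximum of 30 does not come into play for these intervals.

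**Full adherence as written**

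| Situation | Calculation | Score |
|---|---|---|
| One period, *d* = 14, no dose on the return day | 28/15 | 186.7% |
| One period, *d* = 14, dose on the return day | 30/15 | 200% |
| Both NYX-2925 periods, 28 capsules each | 56/(15 + 15) | 186.7% |
| *d* = 10, no return-day dose | 20/11 | 181.8% |
| *d* = 10 to 18, dosed on both end days, enough drug supplied | 2(*d* + 1)/(*d* + 1) | 200% |
| *d* = 18, one bottle only, all 30 capsules taken | 30/19 | 157.9% |

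The placebo period starts at a fixed Day 1. I assume *d* = 11 to 16, that is, the Week 2 visit at Day 14 or 15, ±2 days. With enough drug supplied, full adherence then scores from 22/12 = 183.3% to 200%. With a single bottle at *d* = 16 it scores 30/17 = 176.5%.

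Every value exceeds 125%. With a single bottle, full use does not come down to 125% until *d* = 23 (30/24 = 125%), well outside the windows. With enough drug supplied in the NYX-2925 periods, even 80% adherence scores from 0.8 × 181.8 = 145.5% to 0.8 × 200 = 160%.

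**Who falls inside the band as written**
- One period, denominator 15: 12/15 = 80.0%, 18/15 = 120.0% and 19/15 = 126.7%. So 12 to 18 of the 28 capsules due pass (42.9% to 64.3%). In bottle terms the subject hands back 12 to 18 of 30; a fully adherent subject hands back 2.
- Overall, denominator 30: 24/30 = 80.0%, 37/30 = 123.3% and 38/30 = 126.7%. So 24 to 37 of the 56 due pass (42.9% to 66.1%), with 19 to 32 missed (33.9% to 57.1%). The subject hands back 23 to 36 of 60; a fully adherent subject hands back 4.
- One capsule a day for 14 days scores 14/15 = 93.3% and is classed as compliant.

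**With expected = 2(*d* + 1), capped at capsules dispensed**
- *d* = 10: 20/22 = 90.9%.
- *d* = 14: 28/30 = 93.3%, or 30/30 = 100% with a return-day dose.
- *d* = 18, extra drug supplied: 36/38 = 94.7%, or 38/38 = 100%. One bottle, all taken: 30/30 = 100%.
- One capsule a day for 14 days: 14/30 = 46.7%, correctly below 80%.

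**The case against.** The strongest reply is that the error would reveal itself and does little damage. Almost every adherent subject would land above 125%, and a PP population close to empty should prompt a query. Dispensed and returned counts are on the CRF, so the correct ratio can always be recovered. SAP 6.2 states: "The efficacy population will be the primary analysis population used for this study". That population has no compliance criterion, and the safety population does not use the ratio either. The only PP output that can be seen is in SAP 7.2: "Demographics and baseline characteristics will be summarized for the safety, efficacy, and PP populations". SAP 6.3 also has the sponsor define the PP population by data review before database lock.

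Most of this stands, and it limits the weight of the point. It does not remove it. The action that SAP 6.3 spells out for the review is exclusion ("subjects may be excluded due to particular major protocol deviations"), and it states no way to waive the band for a subject who fails it. A programmer who added the factor without a SAP change would depart from the prespecified derivation. Whether PP efficacy analyses exist cannot be seen, because those sections are redacted.

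Two technical qualifications also stand. The exact score depends on the interval, on the return-day dose and on drug supply, although no combination within the visit windows brings full adherence to 125% or below. And the factor of 2 alone is not quite enough. If a maximum of 30 were kept for a whole period while extra drug was supplied, 18 days of full adherence would read 36/30 = 120% or 38/30 = 126.7%, and the second is outside the band.

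The rule that unreturned drug "will assume that all of that study drug was taken by the subject for analysis purposes" is a separate choice that also pushes scores upward. The error here does not depend on it.

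**Conclusion.** The concern holds. The expected-capsule formula is wrong as written, and it displaces the 80–125% band to about 43–66% true adherence overall. The figure of 186.7% assumes a 14-day interval with 28 capsules taken. The conclusion that full adherence fails the band needs only the two-capsule regimen and the ±2-day windows. That capsules were intended is an inference from the stated maximum of 30, but the units cannot be reconciled otherwise.

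The visible consequences are limited to period and overall compliance, the categorical compliance table, the compliant/non-compliant classification and PP membership. The primary analysis population is unaffected. This should be fixed, but it does not threaten the main analysis.

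**What to change.** Before database lock, replace the derivation in SAP 8.1 with:

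Expected number of capsules = 2 × (date returned − date dispensed + 1), capped at the number of capsules dispensed in that interval (30 when one bottle is issued).

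Use this one definition for period compliance, overall NYX-2925 compliance, the categorical table and the PP criterion in SAP 6.3. Tying the cap to capsules dispensed covers the additional dispensing that SAP 8.1 allows.

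State also whether the return day counts as a dosing day. If it does not and the + 1 is kept, the 80% limit at 14 days is 0.80 × 30 = 24 of the 28 capsules due, which is 85.7% true adherence.

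The cost is one line of SAP wording and one derivation. No new data are needed.

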8.2 Study Drug Exposure

The study will include the following fixed placebo period and active treatment periods with 2 dose strengths:

- Placebo PO QD for 2 weeks
- NYX-2925 20 mg PO QD for 2 weeks
- NYX-2925 200 mg PO QD for 2 weeks

Each bottle number assigned to a subject will be verified that correct study drug was given based on the each treatment period. Any incorrect study drug bottle given where the estimated number of capsules taken defined in [Section 8.1](#) is greater than zero, will be defined as a major protocol deviation. Study drug exposure will be listed and summarized based on the treatment periods the subjects received.

The number of study days of study drug exposure will be summarized using descriptive statistics based on the date of the last dose of study drug collected on the CRF for each treatment period. If the date/time of the last dose of study drug was not fully collected for a treatment period, then the date of returning the study drug will be used instead. If a subject is lost to follow-up after being dispensed study drug and the date of the last dose of study drug was not collected, then the number of study days will be set to missing for that specific treatment period.

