5.1.2 Study Day

Study day will be calculated in reference to Day 1 stated above in [Section 5.1.1](#). For assessments conducted on or after the Day 1 date, study day is calculated as the assessment date – Day 1 date + 1. For assessments conducted before the Day 1 date, study day is calculated as the assessment date – Day 1 date. There is no Study Day 0 in this study.

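### SAP 8.2 counts exposure in days, but its return-date fallback is triggered by an incomplete last-dose date/time, so a known date can be overwritten because only the clock time is missing

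*SAP*

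**What the plan says.** SAP 8.2 (Study Drug Exposure) plans a descriptive summary: "The number of study days of study drug exposure will be summarized using descriptive statistics". Where the count stops in each period is fixed by the words "based on the date of the last dose of study drug collected on the CRF for each treatment period". The end point of the count is therefore a date.

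Two rules for incomplete data follow:

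- Fallback, with its trigger and its substitute in one sentence: "date/time of the last dose of study drug was not fully collected for a treatment period, then the date of returning the study drug" (the return date then replaces the CRF entry).
- Exception, applied period by period: for a subject lost to follow-up after dispensing, if "the date of the last dose of study drug was not collected, then the number of study days will be set to missing".

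The first rule tests the date and time together. The second tests the date alone. The disposition listing in SAP 7.1 also carries a last-dose date and mentions no time. The rules for partial dates in SAP 5.6.3 cover adverse events, medications and medical history, but not last-dose dates, so nothing there overrides 8.2.

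**The concern.** Time of day plays no part in a count of days, yet the fallback makes a missing time sufficient reason to discard a date that is known. The value put in its place is never earlier than the true one, so the error runs in one direction: exposure is kept or lengthened, never shortened. The gap is largest where dosing ended well before the bottle came back.

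The two triggers also leave a hole. A subject lost to follow-up with a recorded date, no time and no returned bottle meets the condition for the fallback but has no return date to use. The same subject does not meet the condition for being set to missing. Two programmers could reasonably code this case, and the blank-time case, differently.

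What is at stake is the accuracy of exposure by treatment period, and of the pooled NYX-2925 column that SAP 5.3 provides for exposure tables, in a study of about 24 subjects.

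**Working it through.** The documents give no figure on this point, so there is none to reproduce. The check is date arithmetic.

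**Inputs**

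- Unit and end point: days, to the last-dose date (SAP 8.2).
- Day count: 8.2 gives no formula, so the convention of SAP 5.1.2 is borrowed as an assumption: "study day is calculated as the assessment date – Day 1 date + 1". The dispensing day is taken as period day 1.
- Dispensing at Day 1, Week 2 and Week 4 (SAP 8.1); target days 14, 28 and 42 (SAP 5.5.1).
- Return visit window: ±2 days (headings of protocol section 10.2). With dispensing on its target day, return falls 12 to 16 days later in a 14-day period.
- Planned subjects: 24 (SAP 4.3).

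**Direction.** Drug cannot be returned before the last dose taken from the returned bottle. The excess is return date minus last-dose date, which is zero or positive. The start date cancels from this difference.

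**Size for one record.** Let L be the period day of the last dose and R the number of days from dispensing to return. The correct count is L, the fallback count is R + 1, and the excess is R + 1 − L.

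| Last dose on period day (L) | Count by fallback, R = 14 | Excess, R = 14 | Excess, R = 12 to 16 |
|---|---|---|---|
| 4 | 15 | 11 | 9 to 13 |
| 7 | 15 | 8 | 6 to 10 |
| 10 | 15 | 5 | 3 to 7 |
| 14 (completer) | 15 | 1 | 0 to 3 (R = 13 to 16) |

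The placebo period runs from Day 1 to target Day 14, so R = 13 and the fallback count is 14. The excesses for L = 4, 7, 10 and 14 are then 10, 7, 4 and 0. A completer returning on schedule thus gains 0 to 1 day.

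**Size for a period mean.** If k of 24 subjects have an excess of e days each, the mean rises by k × e / 24. The documents do not say how many records would trigger the fallback. Taking 1 to 4 subjects with 7 excess days each as an assumed range:

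- k = 1: 1 × 7 / 24 = 0.29 days
- k = 4: 4 × 7 / 24 = 1.17 days

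**After the fix.** If a known date is kept when only its time is missing, the excess for such a record is 0.

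**The case against.** The strongest reply is that the wording may be loose drafting with no practical effect. The sentences on either side of the fallback speak only of a date, as does SAP 7.1, and no public page shows a last-dose time field. If the CRF has none, no known date can be lost. This stands as a limit on the finding, but not as a reason to leave the sentence, because the SAP is what the programmer follows.

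A reader might infer that early stoppers in general are credited with days they did not dose. The documents do not support that. The main rule uses the recorded last-dose date, so an early stopper with a complete entry is counted correctly. Extra days arise only if the entry is incomplete and the drug is returned later, and subjects lost to follow-up with no last-dose date are set to missing.

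A reader might also infer that the capsule count shows when dosing stopped and should replace the return date. It cannot do so reliably:

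- A low count may reflect scattered missed doses. A subject who took 20 capsules with a last dose on day 14 would be cut to 20 / 2 = 10 days.
- The date of first dose was not collected (SAP 5.1.1), and 8.2 states no first-dose date for the later periods.
- Unreturned drug is assumed taken (SAP 8.1). An early stopper who brings back none of 30 capsules would still get 30 / 2 = 15 days.

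Finally, a reader might infer that the safety results are distorted. The planned adverse event tables count subjects and events (SAP 12.1) and assign events to treatment by visit dates (SAP 5.2), not by exposure days. SAP 12.1 uses the final dose for its 30-day window but does not say that the 8.2 fallback applies there. Low capsule use also remains visible in the compliance table of SAP 8.1, which this rule does not change.

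**Conclusion.** The point holds as a minor defect of wording. Followed literally, SAP 8.2 replaces a known last-dose date with the return date when only the time is missing, and the replacement can only lengthen exposure. For an affected record the excess may be about a week or more (8 days for a last dose on period day 7 with return 14 days after dispensing). It is 0 to 1 day for a completer returning on schedule.

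The conclusion rests on three things: the literal reading of the trigger, the day count borrowed from SAP 5.1.2, and the existence of a time field on the CRF, which cannot be confirmed from the public text. The frequency is unknown, so the shift of 0.29 to 1.17 days in a period mean is an illustration under an assumed range. Only the descriptive exposure summary is affected; no efficacy result changes. The documents do not show why subjects would stop early, so no link between this rule and adverse events can be claimed.

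**What to change.** In SAP 8.2, make the fallback depend on the date alone: the return date is used only when the last-dose date itself is incomplete, and a known date is always used whatever the time field holds. Both sentences would then test the same thing, which also closes the gap for a subject lost to follow-up with a known date.

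Flag every return-date value as imputed in the exposure listing, so that a reader can see how many there are.

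Do not impute the last dose from capsule counts. At most, compare the count with the imputed duration as a consistency check and query discrepancies.

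The cost is one changed sentence and one flag variable. One limitation remains: where the date is truly missing, the return date may still overstate exposure, but the flag makes this visible.
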